Once the patient is placed on ECMO, baseline arterial blood gas (ABG), complete blood count (CBC), fibrinogen, platelet count, aPTT, PT and TEG will be performed. Simultaneous heparinase and kaolin TEG must be performed any time a TEG is performed. Pertinent TEG results will include: heparinase-kaolin TEG maximum amplitude (MA) in millimeters (mm), heparinase-kaolin TEG r-time in seconds, heparinase-kaolin TEG alpha angle in degrees, and TEG functional fibrinogen (FLEV) MA in mm. These tests will be performed by a perfusionist in the operating room under the oversight of a co-investigator or principal investigator.

For all patients, the above tests will be performed per the algorithm described in Flowcharts 1 and 2 (attached). Flowchart 1 describes transfusion algorithm for patients in the operating room with inadequate hemostasis, >4 cc/kg/hour. Flowchart 2 describes transfusion management in the ICU when bleeding is less than <4 cc/kg/hour.

Once patient has a normal TEG result with adequate hemostasis, either heparin or bivalirudin will be used as the anticoagulant. Transfusion parameters as described above will only be used on patients who are received no anticoagulation or heparin anticoagulation. If patients are receiving bivalirudin as their anticoagulation strategy, the transfusion parameters with TEG application will not apply.

Heparin titration will be based on kaolin TEG r-time, MA, alpha angle and anti-Xa. Transfusion parameters will be based on heparinase TEG results, INR, platelet count, fibrinogen, and CBC per study protocol.

CTICU heparin titration nomogram:

antiXa/TEG/ACT Action

≤0.20 units/ml and r-time < 10 minutes

-Increase infusion rate by 2 units/kg/hour

-Repeat STAT anti-Xa/TEG 6 hours after rate change

**If the anti-Xa AND TEG do not agree, contact investigator and defer to anti-Xa nomogram for treatment

0.21-0.24 units/ml and

r-time >10 minutes but ≤15 minutes -Increase infusion rate by 1 units/kg/hour

-Repeat STAT anti-Xa/TEG 6 hours after rate change

**If the anti-Xa AND TEG do not agree, contact investigator and defer to anti-Xa nomogram for treatment

0.25-0.35 units/ml and r-time >15 but less than 25 minutes and angle between 20 and 50

(therapeutic range) -No changes in infusion rate

-Repeat STAT anti-Xa/TEG every 6 hours for two consecutive results

If therapeutic, order STAT anti-Xa/TEG daily

**If the anti-Xa AND TEG do not agree, contact investigator and defer to anti-Xa nomogram for treatment

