0.36-0.45 units/ml and r-time >25 minutes and angle <30 -Decrease infusion rate by 1 unit/kg/hour after this hour

-Repeat STAT anti-Xa/TEG 2 hours after rate change

**If the anti-Xa AND TEG do not agree, contact investigator and defer to anti-Xa nomogram for treatment

0.46-0.069 units/ml and r-time >30 minutes and angle < 25 -Hold heparin infusion for 1 hour

-Decrease Infusion rate by 2 units/kg/hour after this hour

-Repeat STAT anti-Xa/TEG 2 hours after rate change

**If the anti-Xa AND TEG do not agree, contact investigator and defer to anti-Xa nomogram for treatment

≥ 0.70 units/ml and no sign of TEG clotting -Hold heparin infusion for 2 hours

-Decrease infusion rate by 6 units/kg/hour after 2 hours

-STAT aPTT/TEG 2 hours after rate change

**If the anti-Xa AND TEG do not agree, contact investigator and defer to anti-Xa nomogram for treatment

TEG anticoagulant parameters based upon:

48. [name]. Personal Communication from [name] from Mayo Clinic from retrospective data analysis. 2014; November.

In addition to using the anti-xa level per the CTICU heparin nomogram as detailed above, TEG will also be used to help manage the anticoagulation, based on kaolin TEG r-time and alpha angle. Goals are set as: TEG r-time between 15 and 20 minutes and TEG alpha angle between 30 and 50 degrees. Heparinase and kaolin TEGs will be drawn each time. The heparinase and kaolin TEGs drawn will be able to show a more complete picture of coagulation, in that the heparin effect will be removed (while a patient is receiving heparin for anticoagulation) and underlying coagulopathy can be treated if found. Further, kaolin TEGs, while patients are receiving heparin, will be used for further anticoagulation management, as discussed above.

NOTE: While the ACT is not used at our institution for guiding anticoagulation therapy, many hospitals use this as the only anticoagulation guide. Thus, it would be appropriate to compare anti-xa as well as TEG to the ACT for the gathering of further data. Each time an anti-xa and TEG is drawn per the protocol, an ACT will also be drawn for study purposes.

Transfusion Parameters:

Hematocrit <22.5% or Hemoglobin <7.5 g/dl transfuse 2 units PRBC and recheck CBC

Platelet Count <100,000/uL or heparinase TEG MA <50 mm transfuse 1 dose of platelets

Signs of bleeding and heparinase TEG r-time >20 mm and an INR > 2.0 with clinical signs of bleeding transfuse 4 units of FFP

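### The top row of the heparin nomogram (anti-Xa 0.70 units/ml or more) orders an aPTT with the follow-up TEG, but every row is entered on anti-Xa and none has an aPTT threshold

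*Combined protocol and SAP*

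**What the plan says.** All references are to the combined protocol and SAP.

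- **Basis of dosing.** Research Activities, item 1, states: "Heparin titration will be based on kaolin TEG r-time, MA, alpha angle and anti-Xa". The nomogram that follows is headed "antiXa/TEG/ACT Action".
- **Follow-up in the two rows just below the top one.** "Repeat STAT anti-Xa/TEG 2 hours after rate change". The three lowest rows also order anti-Xa with TEG, at 6-hour intervals, and the therapeutic row adds a daily check once values are stable.
- **Top row.** After a 2-hour hold and a rate cut, the order is "STAT aPTT/TEG 2 hours after rate change".
- **Tie-break, printed in every row including the top one.** "If the anti-Xa AND TEG do not agree, contact investigator and defer to anti-Xa nomogram for treatment".
- **Text after the table.** It introduces TEG goals with "In addition to using the anti-xa level per the CTICU heparin nomogram as detailed above", so the table is understood there as an anti-Xa nomogram.

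**The concern.** A titration table works as a loop: a result selects a row, the row sets the dose and orders the next test, and that test selects the next row. In five rows the loop closes, because the test ordered is the pair on which the table is entered. In the top row it does not close on the row's own order. Staff who follow the line literally hold a TEG, which is half of what the table asks for, and an aPTT, for which it has no place. They must infer from elsewhere in the plan that an anti-Xa is needed.

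At stake is the clarity of an operative dosing instruction at the highest heparin exposure the table covers. This is not background text, which is why a small wording error deserves correction.

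**Working it through.** There is no sample size or test statistic to reproduce. The check is a row-by-row reading of the nomogram, followed by a search for every use of aPTT or PTT.

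**1. The six rows (Research Activities, item 1)**

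| Row | Anti-Xa entry (units/ml) | TEG entry | Follow-up ordered | aPTT threshold |
|---|---|---|---|---|
| 1 | ≤0.20 | r-time | anti-Xa/TEG | none |
| 2 | 0.21–0.24 | r-time | anti-Xa/TEG | none |
| 3 | 0.25–0.35 | r-time, angle | anti-Xa/TEG | none |
| 4 | 0.36–0.45 | r-time, angle | anti-Xa/TEG | none |
| 5 | from 0.46 | r-time, angle | anti-Xa/TEG | none |
| 6 | ≥0.70 | no TEG clotting | aPTT/TEG | none |

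Counts: rows entered on anti-Xa, 6 of 6. Rows whose follow-up is anti-Xa/TEG, 5 of 6. Rows whose follow-up is aPTT/TEG, 1 of 6. Rows with an aPTT threshold, 0 of 6.

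**2. Every mention of aPTT or PTT in the text shown**

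- Study Aims, item 2: background on an earlier cardiac-surgery trial.
- Research Activities, item 1: baseline panel at the start of ECMO.
- Research Activities, item 1: top row of the nomogram.
- Research Activities, item 1: list of laboratory turn-around times.
- Medical Records, item 1: the same turn-around list.

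That makes 5 mentions, and 0 carry an action level.

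**3. What the ordered pair can and cannot do**

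- The TEG half is usable. A follow-up r-time between 15 and 25 minutes with an angle between 20 and 50, for example, meets the TEG part of the therapeutic row.
- The anti-Xa half stays empty. The table requires both, so no row is fully met.
- TEG alone does not always separate the rows. Row 4 needs r-time above 25 minutes and angle below 30; row 5 needs r-time above 30 and angle below 25. Any TEG that meets row 5 therefore also meets row 4. Only the anti-Xa value tells them apart, and their actions differ: a cut of 1 unit/kg/hour in row 4, against a 1-hour hold and a cut of 2 in row 5.
- The tie-break cannot be applied. It compares anti-Xa with TEG and then follows anti-Xa, so it needs a result the top row does not order.

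**The case against.** The strongest reply is that the anti-Xa will be drawn anyway. Risk and Benefits, item 2, says that standard coagulation testing, naming anti-Xa and ACT, accompanies the TEG and drives management. Research Activities, item 3, lists anti-Xa among the standard-of-care tests. The top row orders a TEG, so on a joint reading an anti-Xa comes with it. This largely stands. It limits the consequence, but it leaves a dosing table that disagrees with those sections.

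A second reply is that the aPTT may be a deliberate extra check. The line lacks the word for repetition that the main follow-up line of the other rows carries, and the flowcharts, which might hold an aPTT rule, are not shown. This cannot be excluded. As printed, however, the aPTT replaces the anti-Xa instead of joining it.

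A third reply is that the column heading is weak evidence. It lists ACT, yet no row has an ACT threshold; likewise MA is named for titration and appears in no row. This is fair. The point rests on the row entries and the tie-break, not on the heading.

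A reader might infer more than the documents support:

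- **That anti-Xa would be omitted after a value of 0.70 or more.** The two sections just cited point the other way.
- **That the study ACT would be missed too**, because the plan says "Each time an anti-xa and TEG is drawn per the protocol, an ACT will also be drawn for study purposes". Risk and Benefits, item 2, places ACT with the TEG alongside anti-Xa, so this does not follow.
- **That harm follows from the size of this row's dose change** ("Decrease infusion rate by 6 units/kg/hour after 2 hours"). That figure describes the rate cut. It says nothing about the effect of the follow-up wording.
- **That the feasibility endpoint is distorted.** The plan counts days on which the algorithm was followed, but the text shown does not say whether nomogram steps are scored, nor how often the top row is reached.

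**Conclusion.** The point holds as a wording error of minor severity. One of six rows orders a follow-up pair that, taken alone, cannot complete the joint anti-Xa and TEG condition for the next dosing step, and the aPTT it names has no action level anywhere in the text shown. The facts of the wording are certain; whether the line is a leftover or was intended is not known.

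The practical effect is probably small, on the assumption that staff draw anti-Xa with each TEG, as other sections suggest. No effect on the trial result is claimed. An aPTT rule in the attached flowcharts, if there is one, would change the reading.

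**What to change.** In the row for anti-Xa of 0.70 units/ml or more, replace the follow-up line with the wording of the two rows below it: "Repeat STAT anti-Xa/TEG 2 hours after rate change". An aPTT may be listed as an additional test. The clinical team should confirm the intent first. If aPTT was meant to steer the dose at this level, the table needs aPTT action thresholds instead.

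The cost is one line of protocol text and its submission as an amendment. Anti-Xa is already run at the site, and no further patients are needed.

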*** Describe the process for identifying the appropriate person to act as proxy for the participant:**

The research staff will look to see who signs the surgical and anesthesia consent on the patient's behalf. The Principal Investigator will then take jurisdiction to ensure that person is in fact the patient's legally authorized representative.

If a Legally Authorized Representative already exists for the patient, study

investigators will confirm legality of the proxy and approach that person for consent. If no LAR is named, study investigators will seek informed consent from the following individuals, in this order: natural or adoptive parent; adult child; adult brother or sister; any other available adult relative related through blood or marriage known and documented to have made decisions for the subject in prior health care settings etc.

*** Will assent be obtained from the participant who has impaired decision-making capacity?**

Yes No

*** Justify why their assent will not be sought:**

If a patient is cognitively available to give assent, then they also would be able to give informed consent and so obtaining assent would not be necessary

Consent Forms

1. Consent Forms:

Document	Category	Date Modified	Document History
View Consent Form(0.01)	Consent Form	8/22/2019	History

Refer to the following templates and instructional documents:

- Guidance - [Consent Wording](#)
- Template - Consent Document - [Short Form](#)
- HRP-090 - SOP - Informed Consent Process for Research
- HRP-091 - SOP - Written Documentation of Consent

Waiver/Alteration of Consent

1. * Select all options that apply to the request to waive the requirement to obtain informed consent:

Review of identifiable medical records

*General Requirements: The Federal Policy (45 CFR 46.116 (d)) as well as guidance issued by the FDA requires the following criteria to be met for a waiver or alteration of consent to be approved with one exception. The FDA does not include a biospecimen provision (Item #4 below). You **MUST** provide a justification addressing how each of the criterion are met for each option chosen in Item #1.*

2. * The research involves no more than minimal risk to the subjects;

To enroll patients into the study, medical records of potential subjects will be reviewed. The medical record will be reviewed and if the patient is eligible, further consent process will be followed. If the patient is not eligible, patient's data will not be stored in the study database except the number of patients screened will be entered and stored within the UPMC firewall in a password protected file and drive

3. * The waiver or alteration will not adversely affect the rights and welfare of the subjects;

Medical record review and further eligibility into the study will not affect the patient's right to any standard therapy and welfare of subjects in anyway. If the patient is not eligible, they will receive standard perioperative therapy by anesthesia/ surgery and patient care team. [name] and other anesthesia team members of the study may provide anesthesia/surgical care/ECMO even if the patient's are ineligible for the study and follow the standard of care

4. If the research involves using identifiable private information or identifiable biospecimens, the research could not practicably be carried out without using such information or biospecimens in an identifiable format (enter N/A for FDA regulated studies);

Identification of potential subjects can be done by speaking with all potential subjects or by selectively identifying potentially eligible patients through medical record review. Medical record review will avoid speaking with all patients who may or may not require ECMO after their surgery. But any medical record review by a physician not directly involved in the patient care requires waiver of consent. Without this waiver, we cannot identify potential research subjects

5. * The research could not practicably be carried out without the waiver or alteration;

We cannot feasibility approach every patient who is having surgery without determining if they qualify beforehand.

6. * Whenever appropriate, the subjects will be provided with additional pertinent information after participation;

We will not acquire any information that will be pertinent to the participant's care

since this Waiver only applies to the this limited recruitment procedure. Only eligibility criteria (inclusion and exclusion criteria) of the patients will be reviewed. No other personnel or individual patient care information will be reviewed

7. * Under what circumstances (if any) will you obtain consent from some of these subjects:

A preliminary and limited assessment of patients medical charts will occur just to exclude patients with clear and certain exclusion criteria. Medical records will be reviewed under a waiver of consent for all subjects. They will provide informed consent prior to enrolling in the study.

Medical Records

1. You are required to submit this study to the Research Informatics Office, Health Record Research Request (R3). Per UPMC Policy HS-RS0005, all research projects that access or involve UPMC electronic protected health information (e- PHI) must be submitted to R3, with the exception of clinical trials that are contracted through the UPMC Office of Sponsored Programs and Research Support (OSPARS).

Complete the R3 intake form available at <http://rio.pitt.edu/services>. An R3 representative will conduct a review. You will be notified once your R3 review is complete or if anything further is needed.

*** Describe the protected health information that will be collected from the covered entity and/or the research derived information that will be placed into the medical records:**

Patient characteristics (sex, age, indication for ECMO, VV or AV ECMO, cannulation sites), chest tube output and overall blood loss, Pre-ECMO anticoagulant drug therapies, number of transfusions required while on ECMO, time between transfusions, type of products transfused, pump exchanges required, oxygenator exchanges, occurrence of pump circuit clotting and clots in the oxygenator, time to weaning from/removal of ECMO, need for surgical intervention of hemorrhage, occurrence of clinical thrombotic or hemorrhagic event, specimen turn-around time for standard labs (CBC, ACT, PT, PTT, anti-Xa, INR, platelet count) and TEG result will be collected from the time patient is enrolled in the trial until ECMO is discontinued.

Electronic Data Management

1. * Will only anonymous data be collected (select **NO** if identifiers will be recorded at anytime during the conduct of the study)?

Yes No

Select all identifiers to be collected during any phase of the research including screening:

Name:		Internet Protocol (IP) Address:	
E-mail address:		Web Universal Resource Locators (URLs):	
Social security #:		Social security # (for Vincent payment only):	
Phone/Fax #:		Full face photo images or comparable images:	
Account #:		Health plan beneficiary #:	
Medical record #:		Device identifiers/serial numbers:	
Certificate/license #:		Vehicle identifiers/serial #/license plate #:	
Biometric identifiers, finger and voice prints: 			

a: Will you be collecting any of the following location data: geographic subdivisions smaller than a State such as street address, city, county, precinct, zip, geocodes, etc.? Yes No

* b: Will you be collecting any date information such as birth date, death, admission, discharge, date of surgery/service? Yes No

c: List any other unique identifying numbers, characteristics or codes related to an individual that are to be collected:

d: Will you be collecting any data subject to the General Data Protection Regulation (GDPR)? Yes No

For ALL identifiable data collected, will you be coding the data by removing the Yes No

* identifiers and assigning a unique study ID/code to protect the identity of the participant?

* Will the data be HIPAA de-identified? Yes No

Identifiable data will be kept in a single encrypted file on the shared (z:) drive behind the UPMC firewall. All other study-related data (such as paper records and data for analysis) will have all identifiers removed. To protect against the possibility of breach of confidentiality, all data collected will be identifiable only by a unique subject ID number, and no personal identifiers will be stored with the data. Linkage files identifying subjects will be stored only in the UPMC server and will be linked to the physical record with a subject code. Physical records will be kept in locked files accessible only by study staff; electronic data will be handled and protected as described above on the UPMC server.

**Briefly describe your plan to store
* coded data separately from the
identifiable data:**

2. During this study, will restricted data as defined by the University's Data Risk Classification matrix (<https://www.technology.pitt.edu/security/data-risk-classification-and-compliance>) be processed, stored, or transmitted?

Yes No

3. * During this study, will sensitive data (<https://www.hrpo.pitt.edu/electronic-data-security>) be collected where disclosure of identifying information could have adverse consequences for subjects or damage their financial standing, employability, insurability, educational advancement, reputation or place them at risk for criminal or civil liability?

Yes No

4. * Select all locations where data will be stored or archived(including e.g., personal / employer laptop or desktop): If you have access to University owned or controlled resources, facilities, or repositories, such as computer servers, please choose that option to comply with the [Research Data Management Interim Policy R1 14](#).

Please note that to address Research Security Requirements, University data must be stored in University owned, controlled, or approved repositories, such as Pitt OneDrive. If UPMC or external electronic repositories must be used, they must be approved by Pitt IT.

Storage Device	Description	Identifiable Data	Sensitive Data	De-Identified/Anonymous Data
View UPMC: Departmental or Hospital Server		yes	yes	yes
View UPMC owned desktop, laptop or other device		no	no	no

5. * Select all technologies being used to collect data or interact with subjects: Technologies selected in this section may require a Vendor Security

Risk Assessment, which can be requested [here](#).

N/A

Data Safety and Monitoring

- 1. * Describe your plan to periodically evaluate the data collected regarding both harms and benefits to determine whether subjects remain safe. The plan might include establishing a data monitoring committee and a plan for reporting data monitoring committee findings to the IRB and the sponsor:**

The following data and safety monitoring plan will be instituted to ensure the safety of the subjects and to maintain the confidentiality of the research data. The principal investigator, co-investigators and study coordinators will perform monthly or quarterly reviews of the accrued data and incidence of adverse effects to ensure validity and integrity of the data and to reassess the benefit-to-risk ratio on a frequent and regular basis. Subject privacy and research data confidentiality will be ensured by reviewing the adequacy of the secure location of where the data is stored and by making sure it is all de-identified with the coded case numbers as described previously. Adverse events, data quality and timeliness of participant recruitment will all be reviewed with the team of investigators, who will determine whether the study should be continued as planned, changed or terminated.

- 2. * Describe your plan for sharing data and/or specimens:**

No data sharing is planned.

- 3. If any research data is collected, stored, or shared in a paper format, address what precautions will be used to maintain the confidentiality of the data:**

Paper-based records will be kept in a secure location, computer-based files will be available to personnel involved in the study through access privilege, whenever possible identifiers will be removed from study-related information, patients' computer medical information will only be available through password access.

Risk and Benefits

1. * Enter all reasonably foreseeable risks, discomforts, hazards, or inconveniences to the subjects related to subjects' participation in the research:

View	Research Activity	Review of Medical Records
	Common Risks	No Value Entered
	Infrequent Risks	No Value Entered
	Other Risks	Breach of confidentiality.
View	Research Activity	Blood Draw From Arterial Line
	Common Risks	No Value Entered
	Infrequent Risks	No Value Entered
	Other Risks	No Value Entered
View	Research Activity	TEG Interpretation
	Common Risks	No Value Entered
	Infrequent Risks	No Value Entered
	Other Risks	It is possible that incorrect interpretation of TEG results could lead to mismanagement of coagulation therapy.

2. * Describe the steps that will be taken to prevent or to minimize risks:

All investigators who will access the identifiable medical records already have normal clinical access to all necessary records, as granted by the privacy office for job-related needs. Thus, only HIPAA trained research staff will be handling this information and this information will be stored in a locked database protected by the UPMC firewall. Additionally, all data generated under this protocol will be monitored and maintained by the principal investigator. Any databases that contain identifiable information will be stored on a departmental drive on the UPMC network created for the principal investigator, and all data will be deidentified according to the HIPPA "safe harbor" guidelines prior to statistical analysis.

In order to avoid coagulation mismanagement as the result of a misinterpreted TEG result, traditional standard of care coagulation testing will also be done (anti-Xa, ACT) in conjunction with the TEG and will be the driving force in coagulation management.

Arterial line blood draws will be limited to the lowest number possible based on previous TEG and conventional test values. The average patient will have a maximum of 15 blood draws over the duration of the trial.

3. Financial risks - will the subject or insurer be charged for any research required procedures?

Yes No

* Address each procedure with a justification and indicate if charges are incurred for investigational drugs/devices. Address, if applicable, a contingency plan for those not able to cover the cost of participation:
Charges will be billed only for procedures performed as part of the subject's routine clinical care.

4. Describe the steps that will be taken to protect subjects' privacy:

Research intervention will be conducted in a private room with the patient, collected information will be limited to that which is necessary for the goals of the research study, access to the patient's private information will be limited to those involved in the patient's medical care.

5. What steps will be taken in the event that a clinically significant, unexpected disease or condition is identified during the conduct of the study:

The patient's primary medical team will be immediately notified of the unexpected, clinically significant condition. The patient's clinically significant medical condition will be managed accordingly. If any of the clinically significant medical condition is related to the study, then the patient's participation in the study will be re-evaluated, with the possibility of the patient being withdrawn from the study if this leads to the resolution of the clinically significant medical condition.

6. Describe the potential benefit that individual subjects may experience from taking part in the research or indicate if there is no direct benefit. Do not include benefits to society or others:

There is no direct benefit to the subjects.

7. Do you anticipate any circumstances under which subjects might be withdrawn from the research without their consent?

Yes No

8. Describe procedures that will be followed when subjects withdraw from the research, including partial withdrawal from procedures with continued data collection and data already collected:

After withdrawing from the study, each subject's data will be kept for the required data retention period in a secure, locked facility, and will be destroyed after that period. Patients' data might be used for data analysis if deemed necessary/useful (e.g. reason of withdrawal).

Conflict of Interest

Institutional Financial Interests

1. * To the best of your knowledge, has the University of Pittsburgh optioned or licensed technology that will be tested or evaluated in this research?

Yes No

Ancillary Reviews

1. Ancillary reviews or notifications selected below are required based on previous answers to questions. If a selection is incorrect, return to the appropriate page and adjust the answers to questions on that page:

- Conflict of Interest (**COI**)
- Clinical and Translational Research Center (**CTRC**)
- Data Security
- Honest Broker
- UPMC Investigational Drug Service
- Pitt Medical School Review
- Pitt+Me
- IND & IDE Support(**IIS**)
- Radioactive Drug Research Committee (**RDRC**)(study involves the evaluation or use of procedures that emit ionizing radiation)
- ORP Business **Manager** (required for industry sponsored studies)
- Religious Directives
- Scientific Review
- Health Record Research Request (**R3**) (required if using UPMC clinical data and authorization for other UPMC data sources for research)
- UPMC Office of Sponsored Programs and Research **Support** (using UPMC facilities and/or UPMC patients during the conduct of the study)

2. Additional ancillary reviews the PI may choose to include as needed for the research:

- Human Stem Cell Oversight (**hSCRO**)
- Institutional Biosafety Committee (**IBC**)(study involves deliberate transfer of recombinant or synthetic nucleic acid molecules)

Good Clinical Practice (GCP) Training

1. * Regardless of funding source, is this study a clinical trial (as defined by the NIH)?

Yes No

ClinicalTrials.gov Information

Visit the University of Pittsburgh Office for [ClinicalTrials.gov website](#) or contact [contact] for further information.

2. * Was this study registered, or will it be registered, on ClinicalTrials.gov?

Yes No

3. * Is the University of Pittsburgh or UPMC the Sponsor Organization for this study record?

Yes No

